Overview. We will conduct a 6-month randomized controlled pilot study with 80 YTM. The goals of the pilot study are to: a) Gain direct feedback from participants about whether and to what degree the MyPEEPS Mobile App worked as intended; b) Assess the acceptability of MyPEEPS Mobile dosing and content for YTM; and c) Observe the flow of procedures, including assessment at baseline, retention efforts, data management, and follow-up assessments. The recruitment plan, screening, and consent/assent processes are described in the Protection of Human Subjects and Clinical Trials Information sections. Our **primary outcome for this study will be:** change in number of condomless receptive anal or vaginal sex acts with sex partners assigned male at birth. **Sampling Approach to Successfully Enroll YTM in this Project.** We will recruit 80 participants from an online national sample and ensure that at least half of our sample is from racial/ethnic minority groups. Using active and passive recruitment methods, the on-site project coordinators will oversee and participate in recruitment efforts. The study staff hired for this project, on-site coordinator, and the peer-to-peer networking efforts will be used to recruit study participants. Our pilot study will comprise a convenience sample through active online recruitment through Instagram, Twitter, Snapchat, and Facebook advertisements. We will use psychographic targeting (in-depth, publicly available consumer data such as interests, city) to advertise only to potentially eligible individuals. We have successfully used this approach to recruit our sample of YMSM in the MyPEEPS project. Through our advertisements, and as previously mentioned, we have screened

>800 YTM who would be eligible for the proposed MyPEEPS study, *and we will plan to recruit them as well as others into the proposed study. We are confident in our ability to enroll the proposed target sample.*

Sample Size and Power Calculation. This study plan is to enroll 80 participants with 1:1 random assignment to the intervention arm and the control arm (i.e., 40 in each arm). Compared to a large-scale randomized trial, we do not expect that this pilot trial will have power to detect many of the

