Study Outcomes. The pilot study will be used to assess the preliminary efficacy of MyPEEPS Mobile for YTM. Our primary outcome will be the number of condomless receptive anal and/or vaginal sex acts with either a cisgender male or transgender woman. To estimate the effect size for a larger clinical trial, we will focus on the primary outcome of: Condomless receptive anal or vaginal sex acts. The measures listed in Table 6 have been used in our MyPEEPS trial and piloted with 49 YTM as part of our formative work for this application. We will collect all measures at baseline, 3 and 6 months, other than demographic variables which will only be collected at baseline. We also ask participants to report on their own knowledge of their most recent partners' use of PrEP or ART medications. Given the unreliability of perceptions of partner-related risk in particular(71), we will use these data for a secondary sensitivity analysis (see below). This study is not powered for efficacy or tests of moderation or mediation; nonetheless, the purpose of the inclusion of these factors is to measure the impact of the intervention on

them as intermediate targets given their potential role in behavior change.

Table 6. Outcome Measures

Demographics

Sociodemographic (e.g., age, race/ethnicity level of education, housing status)

Newest Vital Sign(72)

Short Test of Functional Health Literacy (S-TOFHLA)(73)

Transgender Congruence Scale(74)

Measures of Hormone Use

Primary Outcome Measures

Condomless receptive anal and/or vaginal sex (adapted from AIDS-Risk Behavior Assessment)(68-70)

Intermediate Outcome Measures

Self-efficacy for safer sex and situational temptation for unsafe sex(75)

Condom Errors(76)

Health Protective Communication Scale(77)

HIV-Knowledge Questionnaire – HIV-KQ-18(78)

Alcohol and Substance Use(79)

Sexual Behavior Index(80)

Secondary Outcomes

nPEP and PrEP Use

Self-reported HIV and STI Testing

Partner(s) PrEP Use, PrEP Adherence or Viral Suppression (if partner is HIV+)

Program Evaluation

Knowledge of and beliefs about the content of the MyPEEPS Mobile intervention

MyPEEPS intervention acceptability and tolerability(81)

Paradata

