Data Analysis. All multivariate analyses will be preceded by standard descriptive bivariate analyses to describe key variables and relationships among key variables. These analyses will include means, frequency tables, histograms, and examination of distributions. All statistical tests will be two-sided tests with the level of significance at 0.05(60).

Outcomes: This study will examine whether the intervention will reduce the number of condomless receptive anal or vaginal penile sex with either a cisgender male or transgender woman; the primary outcome is a count measure (Table 6 - Outcome Measures). We assume that all count outcome variables follow Poisson or negative binomial (NB) distribution, $y \sim \text{Poi}(\lambda)$ or $y \sim \text{NB}(\lambda, \kappa)$ and all percentage outcomes follow binomial distribution, $y \sim \text{bin}(n, p)$. Let the expected value of outcome, $E(y) = \varphi$, so $\varphi = \lambda$ for count outcomes and $\varphi = p$ for binary outcomes. We propose the following generalized linear mixed model (GLMM) to analyze all outcomes. The level of analysis

will be assessed at each data point. For person i and data assess wave W (i.e. baseline, 3, and 6 months):

$$+ \mu_i,$$

where $h(\cdot)$ is the link function for the GLMM. We will use log-links (Poisson or NB regression) for count

Table 7. Codes for design variables

Months	Intervention			Delayed Intervention		
	Arm	W	INT	Arm	W	INT
Baseline	0	0	0	1	0	0
3 mos	0	1	1	1	1	0
6 mos	0	2	1	1	2	1

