Sensitivity Analysis: To address whether PrEP use by the partner or the viral suppression status of a HIV+ partner affects the outcome, we will ask participants if their partner(s) use PrEP, use PrEP regularly or if their partner is HIV+ are virally suppressed and we will conduct a counterfactual sensitivity analysis(83, 84), which includes the following steps: 1) We will examine if there is any difference in partners' PrEP use and/or HIV status between pre- and post- intervention. This comparison can be done using the same GLMM for the primary outcome, treating partners' PrEP use and/or HIV status as the outcome. 2) We will examine the impact (or association) of partners' PrEP use and/or HIV status on condomless anal sex based on a GLMM or LMM. 3) If there are difference in step 1) AND significant effects in step 2), our estimation of the impact of intervention on main outcome will be biased. We will correct estimates by estimating the true causal effect of impact on main outcome.

Secondary Outcomes: We will use GLMM to analyze secondary outcomes with appropriate choice of link functions according to the outcomes. All analyses will be done on the final data set (baseline n=80). As an objective of this R34, we will quantify intervention effect sizes of program impact on risky sexual behavior and substance use. To gauge effect sizes, we will use Cohen's d (85) and Hedge's g corrected for sample size(86), both of which express the average amount of individual change between experimental and control groups in terms of units of standard deviation. In addition, we will also estimate the correlations within outcomes across timepoints as the magnitude of this correlation can have significant impact on power to detect effects in repeated measures analyses. These estimates of effect size will enable us to accurately determine the sample size necessary to achieve adequate statistical power in future investigations of program efficacy within this population. We will use the following outcomes to estimate the statistical power for a larger study: (1) number of receptive condomless anal or vaginal sex acts with male partners (e.g., cisgender males and transgender women) during the past 3 months, and (2) number of HIV tests during the past 3 months. We will estimate the statistical power to examine overall effect with the total subjects to conduct stratified analysis to examine the effects in some subgroups (such as by sex and/or for some racial/ethnicity

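### Step 2 of the partner PrEP/HIV-status sensitivity analysis tests only the anal component of the primary outcome, yet its result helps decide whether the main effect is corrected

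*Combined protocol and SAP*

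**What the plan says.** The primary outcome is defined several times, always with vaginal acts included. Section 4.5 (Overview) gives it as "change in number of condomless receptive anal or vaginal sex acts with sex partners assigned male at birth". Section 7.6 (Study Outcomes) states: "Our primary outcome will be the number of condomless receptive anal and/or vaginal sex acts with either a cisgender male or transgender woman". The Data Analysis text of section 7.6 describes the aim as to "reduce the number of condomless receptive anal or vaginal penile sex with either a cisgender male or transgender woman; the primary outcome is a count", which is to be modelled with a log link under a Poisson or negative binomial distribution.

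The Sensitivity Analysis paragraph of section 7.6 opens with its purpose: "To address whether PrEP use by the partner or the viral suppression status of a HIV+ partner affects the outcome". It then has three steps:

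1. Compare partners' PrEP use and/or HIV status before and after the intervention, with the GLMM used for the primary outcome.
2. Look for an association of partner PrEP use or HIV status, with the outcome and model given as "on condomless anal sex based on a GLMM or LMM".
3. If step 1 shows a difference and step 2 shows significant effects, treat the estimated effect on the main outcome as biased and correct it.

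**The concern.** The rule asks a question about one variable and answers it with another. Step 3 concerns the main outcome, but step 2, one of its two conditions, is stated on anal sex alone. Nothing in the documents says that this restriction is intended, and no parallel step covers vaginal acts.

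The omitted component is not marginal by design. Under section 3.2.1 all participants were assigned female at birth, and condomless receptive anal or vaginal penile sex in the past year satisfies the risk criterion, so a person can qualify on vaginal sex alone. Someone who reports only vaginal acts during the study adds a full count to the primary outcome and zeros to step 2 at every wave.

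What is at stake is whether the correction is applied when it should be. The pilot's effect estimate on the combined count is meant to inform the sample size of a larger trial (section 7.6), so a correction wrongly made or wrongly omitted could carry forward.

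**Working it through.** The documents state no size or power for this sensitivity analysis, so there is no figure to reproduce. The check compares the outcome named in each place and then follows the trigger through.

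**Side by side**

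| Place | Acts | Receptive stated | Partner type stated |
|---|---|---|---|
| 4.5, Overview | anal or vaginal | yes | yes |
| 7.6, Study Outcomes | anal and/or vaginal | yes | yes |
| 7.6, Table 6 | anal and/or vaginal | yes | no |
| 7.6, Data Analysis, Outcomes | anal or vaginal | yes | yes |
| 7.6, zero-inflation text | anal or vaginal | yes | no |
| 7.6, outcomes for powering the larger study | anal or vaginal | yes | yes |
| 7.6, Sensitivity Analysis, step 2 | anal only | no | no |

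Step 2 is the only entry without vaginal acts. It is also silent on receptive acts and partner type.

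**Trigger.** A correction is made only if step 1 and step 2 are both positive. Where step 1 shows a difference, step 2 alone decides.

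**Direction.** Write the primary count as Y = A + V (anal plus vaginal acts). Let r_A and r_V be the ratios of mean anal and mean vaginal acts with versus without the partner factor. Let s be the vaginal share of the mean count without it. Dividing the mean of Y with the factor by the mean without it gives

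r_Y = (1 − s) × r_A + s × r_V.

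Step 2 estimates r_A; step 3 needs r_Y. Three cases:

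- Association only through vaginal acts (r_A = 1, r_V = r): step 2 targets 1, while r_Y = 1 + s(r − 1). The association is missed.
- Association only through anal acts (r_A = r, r_V = 1): step 2 targets r, while r_Y = 1 + (1 − s)(r − 1). Step 2 overstates the dependence of the combined count, and more so as s grows.
- Same association for both (r_A = r_V = r): r_Y = r. Step 2 has the right target but uses less of the data.

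These are ratios of marginal means, used to show direction; they do not represent the planned random-intercept model. The documents give none of s, r_A and r_V, so neither size nor sign can be computed.

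**Model.** Section 7.6 assigns count outcomes a Poisson or negative binomial log-link GLMM, extended for excess zeros if needed. Step 2 also permits an LMM without saying when. That leaves an open model choice in a step whose significance helps decide the correction.

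**The case against.** The strongest reply is that this is loose wording. The paragraph's purpose refers to the outcome in general, step 1 refers to the primary-outcome model, and step 3 speaks of the main outcome, so an analyst could read step 2 the same way. Shorthand appears elsewhere: the alternative-design text in section 4.6 calls the outcome variable simply condomless sex. The phrase may also have been carried over from the earlier trial in cisgender young men, whose results in section 1.4 are for condomless anal acts; section 3.6 still calls those randomized YMSM. That origin is an inference. It makes a slip plausible, but it does not change what the rule says.

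Other parts of the reply stand. Step 2 cannot trigger anything without step 1. The analysis is secondary, and section 7.6 itself describes perceptions of partner-related risk as unreliable. The study is stated not to be powered for efficacy, moderation or mediation. The LMM option is a smaller matter than the outcome mismatch.

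Three stronger readings are tempting and are not supported:

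- A reader might infer that step 2 tests an unrelated outcome. It does not: anal acts are a component of the primary count, so the outcome is incomplete.
- A reader might infer that the primary rate ratio will be reported as unaffected by partner protection whenever the trigger fails. The plan does not say what is reported in that case, and the error can run in either direction.
- A reader might put a figure on the power lost in step 2. That would need the anal/vaginal split, a baseline power that the plan never states, and a variance model. Simple Poisson scaling is not safe, because the plan allows negative binomial counts, excess zeros and person-level random intercepts.

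**Conclusion.** The concern holds in a limited form. Step 2 names one component of the primary outcome, while step 3 uses the result to judge and correct the effect on the whole of it. Followed as written, the rule can omit a correction that the combined count needs or prompt one that it does not need. This rests on the text alone and on no assumed figure; the size and direction are unknown. The primary GLMM does not depend on this step. The correction is worth making before analysis because a written decision rule should be run on the outcome it governs.

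**What to change.** In step 2 of the Sensitivity Analysis paragraph in section 7.6, replace *condomless anal sex* with the primary outcome: the number of condomless receptive anal and/or vaginal acts with partners assigned male at birth. State that it is fitted with the same count GLMM as the primary analysis (Poisson or negative binomial, log link, with the same zero-inflation extension if used), and delete the LMM alternative for this outcome.

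The cost is one line of wording. The acts and the partner measures are already scheduled at baseline, 3 and 6 months, so nothing new is collected. The edit aligns the trigger with its target; it does not specify how the step 3 correction is computed, which the plan leaves open.

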outcomes and logit-links (logistic regression) for binary outcomes. μ_i iid~ $N(0, \sigma^2)$ are personal level random effects for the intercept. Variables Arm, W, and INT are design variables. The codes for the design variables are presented in Table 7. Variable Arm is the indicator for intervention arms (0=intervention arm and 1=delayed intervention arm); variable W is data assess wave indicator (0=baseline, 1=3 months, 2=6 months); and variable INT is the intervention indicator (0=pre-intervention, and 1=post-intervention). COV is a vector of personal level covariates at the baseline, such as age, sex, etc., and $\mathbf{XXXXXXXXXXXXXX}$ is a vector of time-dependent covariates assessed at each wave of data for each subject controlling for potential bias between two arms. This model will include both baseline personal level covariates as well as personal-wave level covariates to control for different types of potential confounders. Regression parameter β_3 is the mean value change for the outcome variables between pre- and post-intervention and measures the impact of the intervention on each outcome variable. For the Poisson or NB models, $\exp(\beta_3)$ is the ratio of mean counts (i.e., risk ratio) between post and pre-intervention. For the logistic models, $\exp(\beta_3)$ is the odds ratio between pre- and post-intervention. If the count outcome has excess 0s (for example, much greater than expected number of people who had 0 receptive condomless anal or vaginal sex act as comparison to number of people who had 1,2,..,etc. number of receptive condomless anal or vaginal sex acts), the above Poisson or negative binomial GLMMs can be extended to zero-inflated Poisson or negative binomial models(82).

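### Partner-PrEP sensitivity analysis (section 7.6): the two step 3 conditions do not establish that the main estimate is biased, and step 2 checks anal sex only (minor)

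*Combined protocol and SAP*

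**What the plan says.** The Sensitivity Analysis paragraph of section 7.6 (Data Analysis Plan for Aim 2) sets out three steps.

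- Step 1 fits the primary-outcome GLMM to partners' PrEP use and/or HIV status, to see whether it differs before and after the intervention.
- Step 2 examines the effect or association of partner status "on condomless anal sex based on a GLMM or LMM".
- Step 3 is a rule: "If there are difference in step 1) AND significant effects in step 2", then "our estimation of the impact of intervention on main outcome will be biased". The remedy is: "We will correct estimates by estimating the true causal effect of impact on main outcome".

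The paragraph does not say whether the corrected quantity is a total, direct or indirect effect, and it gives no estimator or assumptions. It calls the exercise a counterfactual sensitivity analysis and cites references 83 and 84, whose titles concern direct and indirect effects and mediation.

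Elsewhere in section 7.6, Study Outcomes states: "Our primary outcome will be the number of condomless receptive anal and/or vaginal sex acts". It makes the partner data material for a secondary sensitivity analysis, warns that perceptions of partner risk are unreliable, and says the study is not powered for mediation. Table 6 lists partner PrEP use, adherence or viral suppression as a secondary outcome.

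**The concern.** Step 3 treats two observations as sufficient for bias. In a randomised comparison they are not. A variable that changes with the intervention and is associated with the outcome has the pattern of a mediator, and the plan's own treatment of partner status as a secondary outcome makes that reading plausible. Leaving a mediator out of the model does not bias the total effect. Putting it in changes the question to a direct effect, which needs assumptions of no unmeasured confounding that randomisation does not supply.

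If both conditions were met in the sample, a report following the plan could label a valid randomised estimate biased and a partner-adjusted one true. Separately, a literal step 2 would leave vaginal acts out of a check on an outcome that includes them.

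**Working it through.** The plan gives no figure for this rule, so there is nothing to reproduce first. The check asks whether the two conditions can both hold while the main estimate is correct. All partner-related inputs are assumptions.

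1. **What the conditions test.** In Table 7, INT is fixed by arm and wave. Step 1 therefore asks whether partner status changes with INT, and step 2 whether partner status goes with sexual behaviour.

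2. **Mediator on the Table 7 design.** Assume a direct RR of 0.70 for INT, partner PrEP of 20% before and 40% after INT, a partner-PrEP RR of 1.6 on acts, no confounding, and the same effect at each wave.
   - True total RR = 0.70 × (1 + 0.6 × 0.40)/(1 + 0.6 × 0.20) = 0.70 × 1.24/1.12 = 0.775.
   - A log-link Poisson model with Arm, categorical W and INT, fitted to the exact expected cell means, gives exp(β3) = 0.775 without partner status and 0.70 with it.
   - Both step 3 conditions hold in truth, there is no bias, and adjustment returns the direct effect.
   - For partner-PrEP RRs from 1.0 to 2.0 and rises in partner PrEP from 0 to 30 percentage points, the unadjusted value equals the true total RR in every cell (0.70 to 0.875).

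3. **A correction that creates an error.** In a two-arm comparison, assume partner PrEP has no effect on acts, but an unmeasured factor U (present in half the participants) raises both. Partner PrEP for U absent/present is 10%/30% in control and 30%/50% with the app. Mean acts are 1/2, multiplied by 0.55 with the app.
   - Unadjusted RR = (0.55 × 1.5)/1.5 = 0.55, which is correct.
   - Control means are (0.45 × 1 + 0.35 × 2)/0.80 = 1.4375 without partner PrEP and (0.05 × 1 + 0.15 × 2)/0.20 = 1.75 with it. App means are 0.55 × (0.35 × 1 + 0.25 × 2)/0.60 = 0.779 and 0.55 × (0.15 × 1 + 0.25 × 2)/0.40 = 0.894.
   - Poisson regression on these cells gives a spurious partner-PrEP RR of 1.19 and an adjusted app RR of 0.531.

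4. **Size.** Section 7.6 gives 87% power for RR 0.55 in subgroups of 64.
   - The implied SE of ln RR is 0.5978/(1.960 + 1.126) = 0.1937. With information proportional to N, it is 0.1733 at N = 80 and 0.0866 at N = 320.
   - Take 0.55 as the total RR, with partner PrEP rising from 20% to 40%. A partner-PrEP RR of 1.5 gives an adjusted value of 0.55/(1.20/1.10) = 0.504. A partner-PrEP RR of 0.667 gives 0.55/(0.8667/0.9333) = 0.592.
   - The 95% CI around 0.55 at N = 80 is exp(−0.5978 ± 1.96 × 0.1733) = 0.39 to 0.77, so both shifts lie within pilot sampling error.
   - Power at N = 320 exceeds 99.9% for 0.504, 0.55 and 0.592. At N = 64 it is about 94%, 87% and 77%.

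5. **How often the trigger could fire.** For 20% against 40% partner PrEP at 3 months (two-sided 0.05), step 1 has about 50% power with 40 per arm and 41% with 32 per arm (0.80 × 40, the retention threshold in Table 5). If both steps must be significant, the rule cannot fire more often than that on the 3-month data. Using all waves would raise these rates. The plan does not say that the step 1 difference must be significant.

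6. **Outcome wording.** Step 2 tests an effect "on condomless anal sex based on a GLMM or LMM". The Outcomes paragraph asks whether the intervention will "reduce the number of condomless receptive anal or vaginal penile sex". Vaginal acts are in the second and not in the first.

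**The case against.** The strongest reply is that this barely matters. It is a conditional branch of a labelled secondary analysis, the trigger depends on sample results that will often be negative at this size, and the effect size for the later trial rests on the primary outcome: "To estimate the effect size for a larger clinical trial, we will focus on the primary outcome". All of that stands and sets the severity.

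Bias can also be read charitably. If the target were behaviour change with partner protection held fixed, the total effect would indeed differ from it. That is coherent, but the plan states no such target, and citing two papers does not choose one.

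The anal-only wording is probably a slip, since the neighbouring paragraphs say anal or vaginal. It is still the current text.

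Four stronger inferences are tempting and are not supported:

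- *That the main estimate cannot be biased.* Chance imbalance, differential attrition or a time trend could produce the same two results, and some of these can bias the estimate. The rule simply cannot tell the cases apart. The balance and attrition checks in section 7.3.2 help with the first two but do not cover a time trend.
- *That the pilot will mislabel its result.* That happens only if both conditions are met in the sample.
- *That the primary GLMM already adjusts for partner status.* It includes a "vector of time-dependent covariates assessed at each wave of data for each subject controlling for potential bias between two arms", but the readable text does not name those covariates.
- *That leaving partner status out is enough to read β3 as the total effect.* This also needs a constant effect across waves. With assumed RRs of 0.55 at 3 months and 0.80 at 6 months in the intervention arm, 0.55 at 6 months in the delayed arm, categorical W and no time trend, the Table 7 model gives exp(β3) = 0.47, outside both.

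**Conclusion.** Minor, and wrong as written. One valid counterexample is enough to defeat an unconditional statement of bias, so the conclusion does not depend on the particular inputs; the sizes quoted do. The mediator examples assume no confounding, and the Table 7 example also assumes a constant effect. Under them the unadjusted estimate is exactly right and the proposed correction moves it to a different estimand; in the confounded example the correction introduces a small error. Any consequence is one of labelling and interpretation in the pilot report. The effect on the overall sizing of the later trial is expected to be negligible; under the assumed inputs a change is visible only in the 64-person subgroups. The step 2 mismatch is a separate, simple inconsistency.

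**What to change.** 1. In step 3, delete the statement that the estimate will be biased, the reference to a true causal effect, and the two-condition trigger. Keep the primary GLMM estimate as the main result.
2. Report any partner-status-adjusted estimate beside it as an exploratory direct-effect analysis. State its estimand and its assumptions of no unmeasured confounding, and repeat the Study Outcomes caveat about the reliability of partner reports.
3. Change the step 2 outcome to condomless receptive anal or vaginal acts.

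The cost is a few sentences in section 7.6 and a small exploratory analysis of data already planned for collection. Data collection and the primary model are unchanged.

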7.5.1 Procedures to Ensure Compliance with Monitoring Plan and Reporting Requirements

Biweekly reports for the sites will be created by the study statistician to review relevant app engagement data, barriers with recruitment/enrollment and retention, laboratory and medical records, compliance with the protocol, and accuracy and completeness of the records. The

investigative team will schedule biweekly conference calls, and these reports will be briefly reviewed by the team. These regular reviews will ensure close communication between the research assistants, quickly identify missing data points, and ensure consistent management of any issues with the protocol between sites.

7.6 Data Analysis Plan for Aim 2

Assessment of feasibility and acceptability of the intervention (Table 5). We have specified the following measures of feasibility and acceptability: Retention Rates, Compliance Rates, Dose, Eligibility Criteria, Recruitment and Enrollment, Missing Data, Study Measures(68-70).

Table 5. Measures of Feasibility and Acceptability of MyPEEPS Mobile for YTM

Constructs	Measures	Threshold (if applicable)
Retention Rates	-How many enrollees remain in the study? -Are they about the same in both arms?	At least 80% will remain in the study.
Compliance Rates	What is the completion rate of app sessions by participants?	At least 80% will have completed at least 75% of the intervention content.
Dose	Is the dose of the intervention e.g., number of sessions adequate (assessment of paradata).	Does the dose need to be adjusted?
Eligibility Criteria	Are eligibility criteria acceptable, or do they need modification because they are too stringent?	Eligibility rates (number of individuals eligible among those approached)
Recruitment and Enrollment	What is the pace of recruitment? Barriers to recruitment and enrollment	
 Rates of refusal (number of refusals vs. enrolled among those approached) Rates of no shows
Missing Data Measures	What is the extent and patterns of missing data? Length of time and burden to the respondents	The survey questions (Number and Type) may need to be adjusted

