subgroups). All power estimations will be based on $\alpha=0.05$ and 2-sided tests. We will base our power estimates on the retention rate at the 3-month and 6-month follow up assessment for each study arm, the intra-cluster correlation.

Given these parameters, if the findings from the pilot study indicate that at post-intervention the number of receptive condomless anal or vaginal sex acts during the past 3 months decreased by 45% or a relative risk (RR) of 0.55, then for a future R01 study, we will have at least 99% power to detect such difference for a total sample size of 320. Secondly, for the stratified analyses, we will have 87% power to detect a relative risk of 0.55 in subgroups with a sample size of 64. For the HIV testing outcome, if the number of HIV tests during the past 3 months increases by 75% (i.e., RR

=1.75), a sample size of 320 participants will have an 84% power to detect such difference.

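### The plan says pilot effect sizes will accurately determine the next trial's sample size; 40 per arm cannot do that, and for counts the effect size named is not on the scale of the power calculation

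*Combined protocol and SAP*

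**What the plan says.** All of this is in section 7.6 (Data Analysis Plan for Aim 2) unless noted.

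- **Effect sizes.** Under Secondary Outcomes, quantifying effect sizes for risky sexual behaviour and substance use is named as an objective of the grant. The measures are Cohen's d and Hedges' g, which "express the average amount of individual change between experimental and control groups in terms of units of standard deviation". The text then states: "These estimates of effect size will enable us to accurately determine the sample size necessary to achieve adequate statistical power in future investigations".
- **Primary model.** The primary outcome is a count, analysed by a log-link mixed model in which exp(β3) "is the ratio of mean counts (i.e., risk ratio) between post and pre-intervention".
- **Future power.** This is conditional on one observed value: "if the findings from the pilot study indicate that at post-intervention the number of receptive condomless anal or vaginal sex acts" fell by 45% (RR 0.55), then "we will have at least 99% power to detect such difference for a total sample size of 320". For stratified analyses, "we will have 87% power to detect a relative risk of 0.55 in subgroups with a sample size of 64". For the number of HIV tests, at RR 1.75, "a sample size of 320 participants will have an 84% power to detect such difference".
- **Pilot size.** Section 7.2 gives 80 participants, 40 per arm. The retention threshold in Table 5 is "At least 80% will remain in the study", or about 64 in total and 32 per arm at the minimum.

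**The concern.** Required sample size varies with the inverse square of the effect size, so a moderately uncertain estimate becomes a very uncertain N. A pilot of this size gives an effect estimate that is moderately uncertain at best. The plan attaches no confidence interval to the estimate and gives future power at single relative risks read from the pilot result.

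The scale is a second gap. For a count, a standardised mean difference mixes the ratio of means with the mean level and the dispersion. It cannot be turned into the RR used for future power unless those two quantities are also known. The plan gives no such link.

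At stake is the intended use of the pilot, which is to support a larger efficacy application. A team that takes the sentence literally could size that trial, or promise subgroup power, on an estimate that happened to be favourable.

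**Working it through.** **Inputs from the documents.** 40 per arm (section 7.2); at least 80% retention, so 32 per arm at the minimum (section 6.2, Table 5); two-sided 5% level, RR 0.55 with 87% power at 64 and at least 99% at 320, RR 1.75 with 84% at 320 (section 7.6).

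**Assumptions.** Observed d = 0.8, no baseline adjustment, 90% target power. The fold-range does not depend on the power target. The mean count, dispersion and correlation behind the stated powers are not given.

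**1. The plan's own figures.** They cannot be rebuilt from inputs, but their consistency can be checked. With power = Φ(|ln RR|/SE − 1.960):
- 87% at 64 implies SE = 0.5978/(1.960 + 1.126) = 0.1937, so V = 64 × 0.1937² = 2.401.
- At 320, SE = √(2.401/320) = 0.0866. Then 0.5978/0.0866 − 1.960 = 4.94, giving power above 99.9%. This agrees with the stated figure of at least 99%.

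**2. Precision of d.** SE(d) = √(2/n + d²/(4n)), n per arm; total N for 90% power = 4(1.960 + 1.282)²/d² = 42.03/d².

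| n per arm | SE at d = 0.8 | 95% CI | Range in N = (upper/lower)² |
|---|---|---|---|
| 40 | 0.2324 | 0.345 to 1.255 | 27 to 354, 13-fold |
| 32 | 0.260 | 0.291 to 1.309 | 20-fold |

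The lower limit reaches zero at d = 0.44 (40 per arm) or 0.50 (32 per arm). Below that, N has no upper limit. The Hedges correction at 40 per arm is a factor of 0.990. It corrects small-sample bias, not imprecision.

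*With baseline adjustment* (assumed correlation 0.6): SE = √(2(1 − 0.36)/40 + 0.64/160) = 0.190. The interval is 0.43 to 1.17, still about 7.5-fold.

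**3. Scale.** Take negative binomial counts with variance μ + kμ², and d as the difference in means over the root mean of the two variances. RR 0.55 then corresponds to:
- control mean 1, k = 4: d = 0.45/√3.38 = 0.24
- control mean 2, k = 1: d = 0.90/√4.155 = 0.44
- control mean 2, k = 0: d = 0.90/√1.55 = 0.72
- control mean 10, k = 0: d = 4.5/√7.75 = 1.62

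The means and k are assumed. The same RR gives very different d.

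**4. RR scale, illustrative only.** Suppose V = 2.401 carries over to the pilot. Then SE at 80 = √(2.401/80) = 0.1733. An observed RR of 0.55 has 95% CI exp(−0.5978 ± 1.960 × 0.1733) = 0.39 to 0.77. The range in N is 13-fold, or 4.8-fold with an 80% interval.

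At the upper limit, 0.772 (|ln RR| = 0.258):
- N = 320: Φ(0.258/0.0866 − 1.960) = 85%
- subgroup of 64: Φ(0.258/0.1937 − 1.960) = 27%

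For HIV tests, the same device gives SE = 0.5596/(1.960 + 0.994) = 0.1894 at 320 and 0.3788 at 80. An observed RR of 1.75 then has 95% CI 0.83 to 3.68, which includes no effect.

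**The case against.** The strongest reply is that this is wording about a trial not yet designed. Nothing in the pilot's conduct or primary analysis depends on it, and the next trial will need its own power section. That is true, and it limits the weight of the point. But effect-size estimation is a declared objective, so the claim made for it should be right.

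The low-power caveats in sections 7.2 and 7.6 do not answer it. They concern detecting effects in this pilot, not using its estimates for planning. The remark in section 7.2 that group means stabilise by 20 to 30 people does not help either: the standard error of d at 40 per arm is still about 0.23.

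Three other replies stand in part:
- **Conditional power.** The future power statement is explicitly conditional and uses RR, never d or g. A reader might infer that d or g went into the 99%, 87% and 84% figures and made them wrong. The documents do not support that; the two are simply unconnected.
- **Assumed inputs.** The d values are mine, and adjustment or repeated measures could narrow the intervals. The RR intervals borrow an undisclosed variance. It would imply about 93% power in this pilot at RR 0.55 with 80 people, which fits poorly with the statement that the pilot is not powered for efficacy.
- **Inputs already planned.** Means, distributions, retention and within-outcome correlations are to be estimated. What is missing is confidence limits and an explicit link to planning.

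**Conclusion.** The accuracy claim is wrong as written. With 40 per arm, even a large observed effect leaves required N uncertain by roughly an order of magnitude: about 13-fold at d = 0.8 unadjusted, about 7.5-fold with an assumed baseline correlation of 0.6. For smaller observed effects there is no upper limit. For counts, the declared effect size does not feed the declared power calculation.

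A reader might infer that 320 is too small for the next trial. The figures do not show that: about 85% power remains at RR 0.77, so 320 is fairly robust for the primary outcome. Nor is 27% a forecast of subgroup power. It shows how quickly the 87% falls within the interval if the borrowed variance holds. That the mean, dispersion and correlation behind the stated powers are not given is missing detail, not an error.

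**What to change.** **Effect-size paragraph (section 7.6, Secondary Outcomes).**
- Replace the claim of accurate determination with a statement that the estimates *inform* the future sample size.
- State that for count outcomes the planning effect size is the between-arm ratio of mean counts at the 3-month primary endpoint, with its 95% confidence interval. Report exp(β3) and its interval alongside. exp(β3) should not serve alone: Table 7 codes the delayed arm as post-intervention at 6 months, so it also draws on data after crossover.
- Keep d and g for scale measures.

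**Future-power paragraph (end of section 7.6).** Present power at 320 and in subgroups of 64 over a range of relative risks that includes the pilot estimate and its confidence limits, instead of at the single observed value. Treat HIV tests in the same way.

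**Cost.** A few sentences and one table, with no change to conduct or data collection. The downside is that quoted power for the next trial, mainly the subgroup and HIV-testing figures, may look less favourable.
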